3.1 Number of Subjects

In the initial safety and tolerability phase of the study, 33 patients will be enrolled on this study, accounting for need for replacement subjects to evaluate endpoints. In the second expansion phase of the study up to 85 patients (including patients from the 1st stage), will be enrolled to obtain additional safety, tolerability and preliminary efficacy of the low dose regimen in selected subsets of patients with myeloid malignancies.

3.2 Replacement of Subjects

As the treatment with HMAs requires extended drug exposure for efficacy, patients who do not complete 12 weeks of therapy for reasons other than disease progression and who do not complete therapy due to toxicity will be replaced. Any patient who starts therapy will be evaluable for safety.

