Rationale	
Noncytotoxic dosing of decitabine given weekly at a dose of 0.2 mg/kg induces depletion of DNA methyltransferase 1 (DNMT1) while minimizing the toxicity and myelosuppression seen with standard HMA dosing regimens. This approach has been shown to be effective in a wide spectrum of patients with myeloid malignancies, including patients with resistant disease such as P53 mutations.
 
Preclinical studies have demonstrated that adding a dose of venetoclax prior to administering decitabine enhances the anti-leukemic activity of HMAs by inhibiting de novo pyrimidine synthesis, which is a major mechanism of resistance to HMA in MDS/AML. Decreasing the dose of venetoclax to a weekly schedule also spares normal myelopoiesis. Therefore, a weekly dosing of decitabine/venetoclax is a very attractive option for a patient population who cannot tolerate or are not known to benefit standard Aza/ven.

Primary Objective	
Primary Endpoint
 
Percentage of participants who are able to continue on treatment without dose interruptions or delays. Defined as delaying or interrupting treatment due to toxicity or intolerance during the induction phase (weeks 1-12)

Secondary Objective(s)	
Secondary Endpoints: (1) Cumulative incidence of response for both CR, CRI and overall response; (2) Event free survival

	
(EFS); (3) Complete remission or complete remission with partial hematologic recovery rate (CR+CRh); (4) Post baseline transfusion dependence rate; (5) Fatigue/quality of life (QoL); (6) Rate of hospitalization; (7) Infection rate
 
Scientific Correlates:
 
Correlation of DNMT1 depletion with clinical response criteria

Sample Size	85 patients
Disease sites/Conditions	Myeloid malignancies: ≥MDS, AML, MDS/MPN overlap syndrome
• Interventions	
 • Venetoclax 400 mg po on days 1, 8, 15 and 28 of each cycle (28day cycle) (+/- 1 day allowed). • Decitabine 0.2 mg/kg SQ on days 1, 8, 15, 22 (for aggressive disease will add decitabine on days 2, 9, 16, 23)

TABLE OF CONTENTS

SUMMARY OF CHANGES	3
ABBREVIATIONS.....	5
STUDY SCHEMA	6
PROTOCOL SUMMARY	7
TABLE OF CONTENTS	9
1.0 INTRODUCTION	12
1.1 BACKGROUND.....	12
1.1.1 Diseases- Myeloid malignancies: Acute Myelogenous Leukemia (AML) and Myelodysplastic Syndromes (MDS) and Myeloproliferative neoplasms (MPN).....	12
1.1.2 Treatment of myeloid malignancies	12
1.2 STUDY RATIONALE.....	14

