- In a retrospective cohort of patients treated at Montefiore-Einstein with this regimen of weekly low dose decitabine/venetoclax (LDDec/VEN) we compared the experience with the low dose regimen to a cohort of contemporaneous patients treated with standard dosing HMA/VEN per the VIALE-A trial (Levitz et al CCR in press) . The ORR for frontline AML and MDS patients for LDDec/VEN was 88% and 64% respectively, similar to the standard dosing regimen. Importantly, we showed that the LDDec/VEN cohort had a much longer time on therapy when compared to patients who received standard VIALE-A dosing (175 vs 78 days; p= 0.014) and a numerical trend toward a higher rate of transfusion independence (53% vs 26%), although this did not reach statistical significance (p=0.33). A preliminary analysis of the data from the initial 17 evaluable patients **enrolled** in this protocol (patients who completed 12 week of induction), demonstrated that only one patient had a dose interruption during induction (one dose held) and no patients required dose reductions. The majority of these patients had AML (n=11) with an ORR of 64% (7/11) and 6/7 responses are ongoing. Given the early high tolerability of the low dose regimen (primary endpoint) and encouraging activity (secondary endpoint), combined with our reported in retrospective data referenced above, adding additional patients in selected subsets of patients will allow further confirmation of the safety and tolerability of this novel low dose metronomic regimen as well as to generate preliminary efficacy data (secondary endpoints) to guide sample size estimates for further clinical development. Data from these additional patients will also help in defining the safety and efficacy profile of this regimen to allow for rationale design of future combination trials using the low dose metronomic HMA/VEN backbone with additional agents to achieve further progress in clinical outcomes for patients with MDS and AML.

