6.3 Criteria for Removal from Study

In the absence of treatment delays due to adverse events, treatment may continue as long as patient is receiving benefit from treatment (see section 6.4), or in the event of the following:

- Disease progression unresponsive to dose adjustment, or progression at maximum dose level
- Intercurrent illness that prevents further administration of treatment,
- The investigator considers it, for safety reasons, to be in the best interest of the subject.
- Any toxicity or adverse event that leads to delay in drug administration of greater than 6 weeks
- Subject decision to withdraw from treatment or from the study

- In accordance with the Declaration of Helsinki and the guidelines of the country of the participating Clinical Study Center, each subject is free to withdraw from the study at any time. An investigator also has the right to withdraw a subject from the study in the event of the patient suffering an intercurrent illness, adverse events, or other reasons concerning the health or well-being of the patient, or in the case of lack of cooperation by the patient. All serious adverse reactions need to be followed until resolution and information returned to study coordinators.
- Should a subject decide to withdraw after administration of study drug, or should the investigator decide to withdraw the subject, all efforts should be made to complete and report the observations up to the time of withdrawal as thoroughly as possible. A final evaluation, the reason for, and the date of withdrawal must be recorded on the CRF. The last visit for each subject will be defined as a study discontinuation/ end-of-study visit, which will occur 30 (± 7 days) days after time of study drug withdrawal.
- Subjects with clinically significant abnormal laboratory values as determined by the investigator or who have ongoing clinically significant treatment related adverse events during their last scheduled clinical evaluation will be monitored and treated until resolution or stabilization is achieved; or, in the event that the subject's condition is not likely to improve because of disease progression, until the cause of the abnormal test result or adverse event can be determined.
- Pregnancy during the course of the study for a child-bearing participant

- Death

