Considerations in choice of primary end-point: The primary end-point is the overall percent of patients who can receive weekly low dose decitabine/ven during the induction period (weeks 1-12) without dose interruptions. The reason for the 12-week time period was used is because responses to HMA/ven are gradual and more so with the low dose regimen. For example, in VIALE-A, the median time to first response (either complete remission or complete remission with incomplete hematologic recovery) was 1.3 months (range, 0.6 to 9.9) and 2.8 months (range, 0.8 to 13.2), respectively.

Considerations in sample-size calculations: As mentioned above, in VIALE-A dose interruptions were required in 72% of patients receiving standard currently approved dosing of Aza/ven. Therefore, the sample size has been calculated to detect a 50% reduction in treatment interruptions, which would suggest that the proposed regimen has a high likelihood of being an advance over the current FDA approved regimen.

Sample size calculations: A Simon 2-stage Optimal design is used to test the null hypothesis of 60% or more patients requiring a dose reduction versus the alternative hypothesis of 36% or less of patients requiring dose interruptions with a one-sided alpha of 5%, power of 80%, and a probability of early termination of 0.77. After assessing dosing of decitabine/ven in 13 patients in the first stage, the trial will be terminated if 7 or more patients require dose reduction. If the trial goes on to the second stage, a total of 33 patients will be studied. If the total number of dose reduction is greater than or equal to 16, the treatment regimen is rejected.

After the 19 patients were enrolled into the study and 17 patients were evaluable after a 12-week induction, there were with no safety concerns. If after a total of 33 patients have been evaluated after the 12-week induction period and show satisfactory results (i.e., fewer than 16 dose reductions during the induction period, so the treatment was not rejected), the proposed amendment for an expansion phase will be implemented in which additional patients will be enrolled to gather more data on the secondary endpoints of efficacy using this regimen in MDS and AML. Background for the rationale for this amendment is outlined in section 1.4. Given the early efficacy seen in the first 11 evaluable patients with AML (64% response rate) and very low toxicity, more subjects will be required to establish the secondary

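### Section 3.2 replaces patients who stop for toxicity before week 12, and nothing keeps them as failures, so the primary interruption count can lose its clearest failures

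*Combined protocol and SAP*

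**What the plan says.** The Protocol Summary gives the primary endpoint as the percentage of participants who stay on treatment without interruption or delay: "Defined as delaying or interrupting treatment due to toxicity or intolerance during the induction phase (weeks 1-12".

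Section 3.2 sets the replacement rule for those who stop before week 12. Its operative words are "reasons other than disease progression and who do not complete therapy due to toxicity will be replaced". Its next sentence is "Any patient who starts therapy will be evaluable for safety". The primary endpoint is not mentioned there.

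Section 6.3 lists among the reasons for removal "Any toxicity or adverse event that leads to delay in drug administration of greater than 6 weeks".

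Section 3.1 says "33 patients will be enrolled on this study, accounting for need for replacement subjects to evaluate endpoints". Section 13 makes the expansion decision conditional as follows: "If after a total of 33 patients have been evaluated after the 12-week induction period and show satisfactory results". It also reports 17 evaluable patients out of 19 enrolled. The rationale for cohort expansion (the second Section 1.4) describes the evaluable patients as "patients who completed 12 week of induction".

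**The concern.** In a trial whose primary question is whether patients can stay on treatment, someone who stops for toxicity during induction is the plainest failure. Section 3.2 as written replaces that patient. Section 6.3 gives a concrete route: a patient removed during induction because a toxicity delay passed 6 weeks has by definition been interrupted, yet meets the replacement rule.

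Being replaced is not the same as being left out of the analysis, so the question is whether any text keeps these patients in the primary count. None does. Section 13 sets no all-treated denominator and no rule for early stoppers. The way the documents use the word evaluable points to completers. If toxicity stops leave the count, the error can only favour the regimen. It affects the 7/13 and 16/33 rules, and also the primary proportion and its 95% confidence interval, which are read against the 72% interruption rate quoted for VIALE-A.

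**Working it through.** **Inputs from Section 13.** Null failure rate 0.60; alternative 0.36; one-sided alpha 5%; power 80%; probability of early termination (PET) 0.77. Stop at 7 or more failures in 13; reject the regimen at 16 or more in 33. The trial therefore continues with at most 6/13 and passes with at most 15/33.

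**Step 1: reproduce the design.** With X1 ~ Bin(13, p) and X2 ~ Bin(20, p):

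- PET(p) = P(X1 ≥ 7)
- Pass(p) = Σ over x = 0 to 6 of P(X1 = x) × P(X2 ≤ 15 − x)

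The results are PET(0.60) = 0.771, Pass(0.60) = 0.0474 and Pass(0.36) = 0.809. The plan's figures are confirmed.

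**Step 2: effect of leaving out replaced toxicity stops.** Let d be the share of all starters who stop for toxicity before week 12 and are replaced. The documents give no value for this regimen, so d is an assumption, shown from 5% to 20%. If these patients are part of the true 60%, the failure rate among counted patients is (0.60 − d)/(1 − d). For d = 0.10 this is 0.50/0.90 = 0.556. Putting that rate into the Step 1 formulas gives:

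| d | Apparent failure rate | PET | Chance of passing |
|---|---|---|---|
| 0 | 60.0% | 0.771 | 4.7% |
| 5% | 57.9% | 0.720 | 7.6% |
| 10% | 55.6% | 0.659 | 12.1% |
| 15% | 52.9% | 0.586 | 18.8% |
| 20% | 50.0% | 0.500 | 28.5% |

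**Step 3: what a just-passing result would hide.** Filling 33 counted places takes 33/(1 − d) starters: 34.7, 36.7, 38.8 or 41.2 for d = 5%, 10%, 15% or 20%. If 15/33 (45%) is observed, the failure rate among all starters is (15 + starters − 33)/starters, which is 48%, 51%, 54% or 56%.

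**Step 4: alternative scenario.** Suppose instead that completers fail at 60% and the toxicity stops come on top. The rate among all starters is then d + 0.60(1 − d); for d = 10% it is 64%. The completers-only count passes such a regimen 4.7% of the time. Counting all starters would pass it 1.6% of the time.

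**Step 5: the trial's own data.** The expansion rationale reports one interruption among 17 evaluable patients: 1/17 = 5.9% (exact 95% CI 0.1% to 28.7%). Nineteen were enrolled, and the documents do not say why two were not evaluable. If both had stopped for toxicity, the rate would be 3/19 = 15.8% (3.4% to 39.6%). That is an upper bound, not an estimate. From 3/19, reaching 16 of 33 would need 13 failures in the next 14 patients.

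**The case against.** The strongest reply is that the documents never say a replaced patient leaves the primary count. Section 3.2 justifies replacement by the drug exposure needed for efficacy and keeps all starters for safety. The primary endpoint is one of tolerability, and Section 13 words it as an overall percentage of patients able to receive weeks 1-12 without interruption. A patient who stopped for toxicity was not able to. The Section 3.2 sentence is also garbled and may have been meant to exempt toxicity from replacement along with progression.

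Both readings are possible, which is why the concern is that the count *can* lose failures. As written, though, toxicity stops are replaced, and toxicity is in any case a reason other than progression. The overall-percentage wording gives no rule for early stoppers, and the same section then bases its decision on patients evaluated after 12 weeks.

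A second reply is that the error rates are hypothetical. This stands in part. The value of d is assumed, and the interim data are far from 60%. Even if the failure rate were 60% from here on, the chance of passing is 99.7% starting from 1/17 (15 of the next 16 would have to fail) and 99.2% starting from 3/19. In the Step 4 scenario the pass rate stays at 4.7%, so alpha inflation depends on the scenario. The two non-evaluable patients may simply not have reached week 12. What remains is the reported primary proportion and its interval. The toxicity monitoring and adverse event tables capture such patients for safety only, not in that proportion.

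A third point also stands: the documents word the primary event in several ways (any interruption or delay, more than two weeks, due to cytopenias, dose reduction). Those passages need reconciling separately.

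**Conclusion.** The concern holds and should be fixed before the primary analysis. Following the rules as written can remove toxicity failures from the primary count, and no text prevents it.

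The size depends on d, which is unknown. For d between 5% and 20%, with the stops forming part of a true 60% failure rate, the one-sided error is 7.6% to 28.5% instead of 4.7%. These figures illustrate how exposed the design is; they do not predict this trial's result. On the data reported so far the go/no-go decision is unlikely to change. The practical consequence is a primary proportion and confidence interval that may be too favourable by an unknown amount. For the first 19 patients the shift is at most from 5.9% to 15.8%.

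Confidence is medium, because the Section 3.2 sentence may have been intended differently.

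**What to change.** - In Section 13, define the primary analysis set as all patients who receive at least one dose.
- Count discontinuation for toxicity or intolerance before week 12 as a failure, including removal for a toxicity delay.
- Take toxicity out of the Section 3.2 replacement rule for the purpose of the primary endpoint.
- Apply 7/13 and 16/33 to the first 13 and the first 33 dosed patients.
- State in advance how patients who stop early for other reasons are counted, with a sensitivity analysis. Report completers only as a sensitivity analysis.
- State why two of the first 19 were not evaluable, and count them as failures only if they stopped for toxicity or intolerance.
- Reconcile the 33 enrolled including replacements (Section 3.1) with the 33 evaluated (Section 13).

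The cost is protocol wording and a check of the reasons for early stops. No extra patients are needed, and alpha 0.047 and power 0.809 are kept. The reported tolerability rate may be slightly less favourable.

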3.3 Expected Duration of Treatment and Subject Participation

In the absence of overt disease progression or dose limiting toxicity, patients would be anticipated to remain on treatment for at least 12 weeks. After 12 weeks, patient may continue therapy if felt to be experiencing clinical benefit.

4.0 PATIENT SELECTION

Each of the criteria in the sections that follow must be met for a subject to be considered eligible for this study.

Subject's Name _____

Medical Record # _____

Research Nurse / Study Coordinator Signature: _____

Date _____

Treating Physician [Print] _____

Treating Physician Signature: _____

Date _____

4.1 Inclusion Criteria

Subjects must meet all of the following inclusion criteria to be eligible for enrollment:

1. Patient must have a diagnosis of MDS, AML, CMML or MDS/MPN with a histopathologic diagnosis confirmed by hematopathology review

AND

2. Indication for therapy with potential sensitivity to HMA therapy, defined as prior published evidence of response to HMA.

AND

3. Patients must be 18 years of age or older

AND

4. Patients must have an ECOG performance status of ≤ 3

AND

5. Patients must have adequate end organ function defined as.

- AST and ALT $< 4 \times$ the upper limit of normal (ULN)
- Bilirubin $\leq 2 \times$ the ULN. If elevated bilirubin is due to impaired conjugation (e.g. Gilbert's disease or concomitant medication) or disease related hemolysis, then direct bilirubin $\leq 1.5 \times$ the ULN.
- As decitabine and venetoclax have little renal metabolism, and have proven safety even in dialysis patients, renal function with a creatinine clearance ≥ 30 mL/min or on dialysis is allowed.¹⁸

AND

6. Subjects must have the ability to understand and the willingness to sign a written informed consent document and complete study related procedures.

4.2 Exclusion Criteria

1. APL
2. Core binding factor AML who are candidates for intensive chemotherapy
3. Prior Treatment with azacitidine, decitabine or venetoclax

4. No other disease directed therapy, save for hydroxyurea, cytarabine, Cladribine, Gemtuzumab ozogamicin including experimental or investigational drug therapy for 14 days prior to study entry.
5. Currently pregnant or breast-feeding. Females of child bearing (FOCBP) potential must have negative serum pregnancy test within 72 hours from treatment start. (NOTE: FOCBP is any biologic female, regardless of sexual or gender orientation, having undergone tubal ligation, or remaining celibate by choice, who has not undergone a documented hysterectomy or bilateral oophorectomy or has had a menses any time in the preceding 12 months (therefore not naturally post-menopausal for > 12 months)
6. Uncontrolled intercurrent illness that could limit life expectancy or ability to complete study correlates. This includes, but is not limited to:
 - a. Ongoing or active infection. As patients with myeloid malignancies are prone to infections, if patients are actively being treated with appropriate antibiotics or antifungal therapy with clinical evidence of infection control, then they will be considered eligible for study.
 - b. Uncontrolled concurrent malignancy
 - c. Congestive heart failure of NYHA class III/IV. Patients with compensated heart failure are permitted.
 - d. Unstable angina pectoris
 - e. New or unstable cardiac arrhythmia. Stable or controlled arrhythmias are permitted
 - f. Decompensated liver cirrhosis (Child-Pugh score ≥ 12 or a MELD score ≥ 21)
 - g. Psychiatric illness/social situations that would limit compliance with study requirements.
 - h. Any other prior or ongoing condition, in the opinion of the investigator, that could adversely affect the safety of the patient or impair the assessment of study results.
7. WOCBP and males that are unwilling to agree to use dual contraceptive measures (i.e., hormonal or barrier method of birth control; abstinence, condom) prior to study entry and for the duration of study participation.

Should a female subject become pregnant or suspect she is pregnant while participating in this study, she should inform the treating physician immediately

8. Sexually active male who is unwilling to use a condom when engaging in any sexual contact with a female with child-bearing potential, beginning at the screening visit and continuing until 4 weeks after taking the last dose of Decitabine/venetoclax.
9. Patients with uncontrolled active HIV infection, as this will further increase the risk for opportunistic infections. However, patients with HIV with undetectable viral load by PCR, without opportunistic infection, and on a stable regimen of antiretroviral therapy would be eligible.
10. Known allergy or hypersensitivity to any component of decitabine or venetoclax formulations

4.3 Inclusion of Women and Minorities

Men, women and members of all races and ethnic groups are eligible.

5.0 REGISTRATION

Subjects will be recruited at Montefiore/Einstein Cancer Center, University of California Davis, and White Plains Hospital Center for Cancer Care. All subjects who have been consented are to be registered in REDCap. Database. For those subjects who are consented, but not enrolled, the reason for exclusion must be recorded.

All subjects will be registered through Montefiore/Einstein Cancer Center and will be provided a study number by contacting the study coordinator listed on the cover page.

6.0 TREATMENT PLAN

6.1 Treatment Regimen Overview

Administration: Decitabine is reconstituted with 5 ml sterile water to facilitate subcutaneous administration. Decitabine is given by subcutaneous injection. Venetoclax is taken as a tablet prepared by patients pharmacy.

Venetoclax is given at a dose of 400 mg po once per week concurrently with the Decitabine dose (+/- 1 day allowed).

All treatment regimens may be continued indefinitely.

Concomitant Treatment: Hydroxyurea is permitted to control leukocytosis and thrombocytosis. In patients with aggressive high bulk disease as determined by the investigator and PI, may receive debulking chemotherapy with either Gemtuzumab ozogamicin, Cladribine or Cytarabine prior to starting decitabine/venetoclax. Also patients who have mutations in either FLT3 (ITD or TKD), JAK2, IDH1 or IDH2 mutation may receive concomitant inhibitors (as outlined in the table below) at any point during the protocol as determined by the PI. Other than HU and above mentioned drugs, no other concomitant disease modifying therapy is permitted. No additional investigational study is permitted and concurrent participation in other interventional trials are not permitted. Participation in registry or non-interventional studies is permitted.

Mutation	Medication
FLT3 ITD	Midostaurin Gilteritinib Quizartinib
FLT3 TKD	Midostaurin Gilteritinib
IDH1	Ivosidenib Olutasidenib
IDH2	Enasidenib
JAK2	Jakafi

Induction phase: The initial 12 weeks of therapy is considered an induction phase during which dose modifications or holds are discouraged except for severe toxicity severe, non-hematologic adverse events, as per figure study schema. However, if myelosuppression from medications are suspect, treatment holds and dose modifications may be considered in consultation with the study chairs. Desired treatment holds or dose modifications should be reviewed as soon as possible with the study chairs to determine whether dose hold/modification is acceptable. The purpose of the induction phase is to produce relatively rapid reduction of tumor burden to a level that will permit recovery by more functional hematopoiesis that can relieve cytopenias.

Long Term Treatment phase: After a 12 week induction phase, persistent treatment without holds could result in severe, treatment related cytopenias. Conceptually, targeted DNMT1 depletion may result in differentiation that could result in hematologic improvement with evidence of persistent marrow disease. Full response to therapy may not occur within 12 weeks as sometimes six months or longer is required for maximal response to HMAs. Thus, the goal should be to maintain dose while ensuring optimal hematologic improvement from therapy.

